Study Title: Nasal vs. Oral Intubation for Neonates Requiring Cardiac Surgery

University of Virginia IRB for Health Sciences Research Protocol #20789

Principle Investigator: [name]

Document Type: Protocol

Document Date: 6/14/18

PROTOCOL

Background

1. Provide the scientific background, rationale and relevance of this project.

Neonates requiring cardiac surgery early in infancy frequently develop feeding difficulties including problems reaching full volume nutrition and transitioning to oral feeds. This is a particular challenge because adequate nutrition status is associated with improved outcomes for these patients. Feeding difficulties are multifactorial, and may arise due to prolonged post-operative intubation, surgical complications, or delay in initiating enteral nutrition. This results in longer hospitalizations, and need for invasive feeding interventions like nasogastric or gastrostomy tube feedings.

Kogon et al. (2007) conducted a retrospective review of 83 infants requiring cardiac surgery in their first 15 days of life. They found that 44.6% of these infants had difficulty transitioning from gavage to oral feeds. 9.6% of infants required invasive procedures (gastrostomy tube, Nissen fundoplication) to facilitate feeding. They identified increased risk adjusted congenital heart surgery (RACHS) score and prolonged intubation as risk factors for delayed transition and need for additional feeding procedures. Single ventricle physiology and presence of a shunt were additionally identified as risk factors for additional feeding procedures.

Piggott et all (2018) conducted a retrospective review of 79 neonates who required the Norwood procedure for congenital heart disease in their first 30 days of life. Of these patients, 59.5% required gastrostomy tube placement for feeding before discharge. They identified vocal cord dysfunction and longer duration of postoperative sedative/narcotic infusion as risk factors for gastrostomy tube placement. Patients who required gastrostomy feedings had a significantly longer hospital length of stay.

Skinner et al. (2005) conducted fiberoptic laryngoscopy in 33 neonates after Norwood single ventricle palliation compared with 18 infants after aortic arch reconstruction as part of biventricular repair. In the Norwood group, 48% of infants had some degree of swallowing dysfunction. 9% of Norwood infants were diagnosed with left vocal cord paralysis, 24% had aspiration on barium swallow, and 18% of infants required gastrostomy tube placement for feeding. In the aortic arch reconstruction group, 25% of infants were diagnosed with left vocal cord paralysis, 35% had aspiration on barium swallow, and 11% required gastrostomy tube placement for feeding. They concluded that vocal cord paralysis and aspiration occur in similar frequencies in neonates regardless of single or biventricular repair.

Both oral and nasal intubation routes are considered safe and acceptable in neonates. However, there have been only a few head-to-head trials to compare the two routes to each other in this population. Spitzer et al. (1982) conducted a trial of 86 neonates requiring intubation for mechanical ventilation. Infants were randomized to oral or nasal routes of intubation. The study found that nasally intubated infants had higher rates of post-extubation atelectasis. However, after accounting for weight, they found that the higher risk of post-extubation atelectasis was only present in infants < 1500 grams. Infants > 2500 grams (term size) were not at higher risk of post-extubation atelectasis. There was not a difference in the risk of local trauma (nasal erosions for nasal intubation, palatal groove formation for oral intubation) between groups. McMillan et al. (1986) conducted a trial of 91 neonates requiring intubation for mechanical ventilation. Infants were randomized to oral or nasal routes of intubation. In this study, nasal intubation was unsuccessful in 6 patients, who were subsequently successfully orally intubated without complications. They did not find increased risk of post-extubation atelectasis, endotracheal tube blockage, or accidental extubation in nasal compared to oral routes of intubation.

While both routes are safe and routinely used by cardiac anesthesiologists at UVA, there are several proposed advantages to nasal intubation in the neonatal cardiac population. Firstly, nasotracheal tubes are more comfortable to the patient as well as more easily secured. Because of this, thus patient requires less sedation to prevent accidental extubation. Secondly, without an oral endotracheal tube in place, the infant is able to practice non-nutritive sucking skills in preparation for oral feeding. A study by Pinelli et al. (2005) showed that non-nutritive sucking helped premature infants more quickly transition from gavage to oral feeding. With lower sedation and oral skills development, we believe that nasally intubated patients will more quickly learn to orally feed and avoid the need for gastrostomy.

Objectives/Hypothesis

Hypothesis: Nasotracheal intubation will allow for lighter sedation in the post-operative period as well as more rapid development of oral feeding skills for infants with congenital heart disease.

Primary outcome measures:

1) Time from surgery to full oral feeds.

Secondary outcome measures:

- 1) Dosage of sedating medications required post-operatively.
- 2) Hospital length of stay.
- 3) Need for tube feeds at discharge (NG or gastrostomy).

Study Design: Biomedical

1. Will controls be used?

No. Participants will be randomized to an intervention - either oral or nasal intubation. All infants will be intubated for surgery, so there is not a control group.

► **IF YES, explain the kind of controls to be used.**

Answer/Response:

2. What is the study design?

Randomized control study

3. Does the study involve a placebo?

No, participants will receive either oral or nasal intubation, both routes are considered safe and acceptable in neonates.

► **IF YES, provide a justification for the use of a placebo**

Answer/Response:

Human Participants

Ages: <2 weeks at the time of surgery

Sex: Male and female

Race: All

Subjects- see below

1. Provide target # of subjects (at all sites) needed to complete protocol.

Version Date: 06/14/18

Page Number: 3 of 8

A sample of 40 neonates in each group, for a total of 80 neonates, is required to have sufficient statistical power.

2. Describe expected rate of screen failure/ dropouts/withdrawals from all sites.

We anticipate that 10% of neonates will be unobserved on the primary outcome due to post-operative complications including need for ECMO or CPR >5 minutes.

3. How many subjects will be enrolled at all sites?

44 participants per group, for a total of 88

4. How many subjects will sign a consent form under this UVa protocol?

88 participants.

Inclusion/Exclusion Criteria

1. List the criteria for inclusion

- Patient is a neonate requiring cardiac surgery
- Patient is <2 weeks of age at the time of surgery
- Includes families who are educationally or economically disadvantaged
- Includes non-English speaking families

2. List the criteria for exclusion

- Patient has an estimated gestational age <37 weeks at the time of surgery
- Patient has known oro-facial or gastrointestinal anomalies
- Patient has known congenital or acquired devastating neurologic injury
- Patient was intubated for >5 days pre-operatively
- Patient required >5 minutes of CPR pre- or post-operatively
- Patient requires ECMO pre- or post-operatively
- Patient remains intubated two weeks post-operatively.
- Excludes infants >2 weeks of age at the time of surgery and other vulnerable populations including pregnant women, fetuses, prisoners, cognitively impaired

3. List any restrictions on use of other drugs or treatments.

None.

Statistical Considerations

1. Is stratification/randomization involved?

Yes.

► IF YES, describe the stratification/ randomization scheme.

Patients will be randomized to oral or nasal intubation using a block randomization scheme generated by a UVA statistician to generate equally sized oral and nasal groups. The concealment envelope with group assignment will be opened by the anesthesiologist, CRNA, or resident performing intubation at the time of surgery. After intubation, this intervention is impossible to blind. The research team and family will be able to see which group the patient is part of.

► IF YES, who will generate the randomization scheme?

Sponsor
 UVa Statistician. [name]
 UVa Investigational Drug Service (IDS)
 Other: Answer/Response:

2. What are the statistical considerations for the protocol?

The null hypothesis to be tested is that the mean number of days to full oral feeding is the same with oral or nasal intubation. The alternative hypothesis is two-sided, and states that the mean number of days until full oral feeds differs between oral and nasal intubation.

3. Provide a justification for the sample size used in this protocol.

Preliminary data on 8 neonates yielded an average of 13.5 from surgery to NG tube removal, with a standard deviation of 11.7. With 40 participants per group, the two-sample t-test with unequal variances yields 80% power, with a 2-sided significance level of 5%, when the mean difference in time to oral feeding is 6 days. In this calculation, we assumed that the coefficient of variation is the same in the nasal and oral intubation groups, meaning that the within-group standard deviation is proportion to the mean. Allowing for 10% dropout/withdrawal yields a sample size of 44 per group, for a total of 88 participants.

4. What is your plan for primary variable analysis?

Initial analyses will use the two-sample t-test, and the associated confidence interval, to compare the groups. Secondary analyses of the primary outcome, the number of days until full oral feeding, will be based on negative binomial regression. In addition to providing an unadjusted comparison of the groups, the use of negative binomial regression will also allow us to estimate the difference between the groups adjusting for covariates, such as the RACHS score (estimates risk of cardiac surgery). While we anticipate that the randomization will balance the distribution of these covariates between the groups, the use of these covariates in a model can improve the precision in estimating the difference between the oral and nasal intubation groups.

5. What is your plan for secondary variable analysis?

A two-sample nonparametric test will be used to compare the average dosage of sedating medications required post-operatively. For hospital length of stay, analyses similar to those described above for days until full oral feeding will be used. The third secondary outcome is a binary variable, indicating the need for tube feeds at discharge. The chi-square tests will be used to compare the proportion of participants in each group requiring tube feeding at discharge.

6. Have you been working with a statistician in designing this protocol?

Yes

IF YES, what is their name?

[name]

7. Will data from multiple sites be combined during analysis?

No

INSTRUCTIONS: IF YES, answer the following questions

7(a). Does the study involve randomization?

Answer/Response:

IF YES, will randomization be done at each site or among sites?

Answer/Response:

7(b). Has the sample size calculation considered the variation among sites?

Answer/Response:

7(c). When combining the data from multiple sites to assess the study results, is the effect of the treatment to be tested (or the association to be tested) assumed to be the same across sites or vary among sites? What is the modelling strategy?

Answer/Response:

7(d). Is there a common protocol used in all sites?

Answer/Response:

IF NO, how will differences among sites, such as those related to the implementation, inclusion criteria, patient characteristics, or other sites characteristics, be considered to assess the study results?

Answer/Response:

Study Procedures-Biomedical Research

1. What will be done in this protocol?

Potential subjects will be identified in the weekly Pediatric Cardiothoracic surgical conference. Subjects' parents will be approached as part of routine pre-operative discussions regarding surgical timing and post-operative expectations. Parents will be introduced to the study, and consented at that time. This will typically take place in the week before surgery, barring emergent changes to the surgical schedule.

Neither oral nor nasal intubation are done purely for research purposes in this protocol. Intubation is a standard and necessary part of the planned cardiothoracic surgery. The cardiac anesthesiologists and CRNAs are experienced in both methods. Typically, the decision of which route is based on clinician decision after assessing the patient. Studies by Spitzer (1982), McMillan (1986), and Xue (2007) demonstrate that both routes are safe in children. Any neonatal intubation carries risk of local trauma, desaturation, and bradycardia. The additional risk of oral intubation is palatal grooving. The additional risks of nasal intubation include nasal ulcers and the possibility of post-extubation atelectasis in infants <1500 grams. Nasal intubation takes slightly more time than oral intubation.

After enrollment, the patient will be randomized with assignment in a sealed envelope. On the day of surgery, the envelope will accompany the patient to the operating room. The anesthesiology team will open the envelope and proceed with the assigned intubation method (oral or nasal). The CRNA or anesthesiologist will intubate using the UVA standard of care. If nasal intubation is complicated by unexpected anatomy (such as choanal atresia), or if the patient cannot tolerate the

longer time required for nasal intubation, then they will be orally intubated for patient's safety. These patients will remain in the study and will be analyzed in the oral intubation group. Intubation route does not affect the subsequent surgery.

The patient will arrive to PICU intubated. The electronic medical record will be used to collect data regarding surgical variables, post-operative sedation needs, and feeding outcomes. The treatment of these patients post-operatively will follow the standard of care PICU procedures, without differences based on study assignment. The post-operative protocols are described briefly here: Sedation needs are determined by standardized sedation scores and nursing protocols. Feeding advances are determined by standardized PICU protocol, with alterations based on RN and MD clinical assessment. The patient will be extubated when clinically appropriate, based on PICU MD assessment. After extubation, the patient is assessed by a Speech-Language Pathologist who determines the patient progress with oral feeding. Data will be collected through hospital discharge.

2. If this protocol involves study treatment, explain how a subject will be transitioned from study treatment when they have completed their participation in the study.

This protocol does not involve an experimental treatment. Both oral and nasal intubation are safe methods, and both are routinely used by the pediatric cardiac anesthesiologists at UVA. After intubation, the remainder of the infant's intra- and post-operative care will proceed by the standard of care. The subject will be extubated when clinically appropriate as determined by the PICU MD. If the patient requires emergent re-intubation while in the PICU, it will be performed orally. Patients who are re-intubated will remain part of the study as long as they do not meet other exclusion criteria (ex. Intubated >2 weeks, >5 min CPR, ECMO).

Subject Compliance with Study Procedures

1. Explain how the study team will monitor the subject for compliance with the study procedures.

The study anesthesiologists will perform the procedure. There is no need for the patient or family to comply.

2. Describe criteria for when a subject is considered to be non-compliant with study procedures.

There is no need for the patient or family to comply. All procedures are performed by the study team.

Bibliography

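### Infants are excluded after randomisation for post-operative events, above all for still being intubated at two weeks, so the groups analysed are not the groups randomised

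*Protocol*

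**What the plan says.** Allocation comes before surgery. Study Procedures, item 1, states: "After enrollment, the patient will be randomized with assignment in a sealed envelope". The envelope is opened in the operating room at intubation.

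The exclusion list (Inclusion/Exclusion Criteria, item 2) nevertheless includes three conditions that arise, or can arise, after that point:

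- "Patient required >5 minutes of CPR pre- or post-operatively"
- "Patient requires ECMO pre- or post-operatively"
- "Patient remains intubated two weeks post-operatively"

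Study Procedures, item 2, confirms that these act on infants already in the trial. Re-intubated infants stay in "as long as they do not meet other exclusion criteria (ex. Intubated >2 weeks, >5 min CPR, ECMO"). The section on expected dropout treats ECMO and CPR cases as having no primary outcome and covers them with a 10% allowance; it does not name two-week intubation. No section keeps any of these infants in the primary analysis.

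On blinding, Statistical Considerations, item 1, says: "After intubation, this intervention is impossible to blind". On care after surgery, Study Procedures, item 1, says: "The treatment of these patients post-operatively will follow the standard of care PICU procedures, without differences based on study assignment". It adds: "Sedation needs are determined by standardized sedation scores and nursing protocols". Extubation is left to the judgement of the PICU physician.

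**The concern.** Randomisation protects a comparison only if infants are not dropped for things that happen after allocation. Here they are, and one of the grounds is tied to the primary outcome, time from surgery to full oral feeds. An infant on the ventilator without a break until day 14 has an outcome above 14 days, against a pilot mean of 13.5. For those infants the rule removes only values from the upper part of the distribution. The Background also cites prolonged intubation as a risk factor for delayed oral feeding.

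Route could influence who is removed. The protocol hypothesises lighter sedation with the nasal route, and extubation is decided by staff who can see the route. If more oral infants are removed, a nasal benefit is understated; if more nasal infants are removed, it is overstated. If the shares are similar the bias is small, but the result then describes only infants extubated within two weeks, and nobody can identify those infants when the route is chosen.

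For ECMO and CPR no link to route is shown. The concern there is only that the as-randomised population is lost.

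**Working it through.** **Timing.** Randomisation follows enrolment and precedes surgery. The two-week criterion cannot be assessed until 14 days after surgery. Post-operative ECMO and CPR are likewise later than allocation. All three therefore act on infants already randomised.

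**The plan's own figure.** Inputs from the sample size justification: mean 13.5, SD 11.7, difference 6 days, constant coefficient of variation, 40 per group, two-sided 5%. The nasal mean is 13.5 − 6 = 7.5 and its SD is 7.5 × 11.7/13.5 = 6.5. The standard error is √(11.7²/40 + 6.5²/40) = 2.12, and Welch power from the noncentral t is 79.7%. The stated 80% reproduces.

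**Illustration of removal.** These are assumptions, not protocol figures:

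- times follow gamma distributions with the means and SDs above;
- the 8 pilot infants describe the population before exclusion, which the protocol does not say;
- removed infants are a random draw from those above 14 days, which is right only for continuous intubation;
- the removal shares are chosen for illustration.

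From the gamma distributions:

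- oral: P(T > 14) = 0.369, E[T | T > 14] = 25.37
- nasal: P(T > 14) = 0.140, E[T | T > 14] = 20.11

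The mean after removing a share p is (mean − p·E)/(1 − p). For 10% oral: (13.5 − 0.10 × 25.37)/0.90 = 12.18. For 3% nasal: (7.5 − 0.03 × 20.11)/0.97 = 7.11. The difference is 5.07. Power below is for the Welch test with 44 randomised per arm; the comparator loses the same shares at random.

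| Removed, oral / nasal | Difference left (true 6) | Power | Power, random loss |
|---|---|---|---|
| 3% / 3% | 6.02 | 84.4% | 82.3% |
| 5% / 5% | 6.04 | 85.2% | 81.4% |
| 5% / 3% | 5.77 | 81.2% | 81.6% |
| 7% / 3% | 5.50 | 77.5% | 81.0% |
| 10% / 3% | 5.07 | 71.1% | 79.9% |
| 3% / 5% | 6.30 | 87.9% | 82.1% |

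In the 10%/3% row the SDs after removal are 11.01 and 6.11, the group sizes 39.6 and 42.7, and the standard error 1.98. That row removes 0.10/0.369 = 27% of oral and 0.03/0.140 = 21% of nasal infants above day 14. The 3%/5% row removes 8% and 36%. With log-normal instead of gamma times, 10%/3% gives 5.13 days.

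A simulation of 100,000 trials with the actual Welch test gave, for 10%/3%, a difference of 5.07 and rejection in 74.9% of trials against 83.8% with random loss.

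**No true effect** (both arms 13.5/11.7). Removing 10% of oral and 5% of nasal infants leaves 12.18 against 12.88, a spurious 0.69 days against the nasal route. With standard error 11.7 × √(2/40) = 2.62, the two-sided error is 5.8% (5.9% with the SDs after removal). Removing 5% and 3% creates 0.26 days and an error of 5.1%.

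**The case against.** The strongest reply is that the numbers are small. Equal removal leaves the difference almost untouched and even raises power slightly. A 5%/3% split costs 0.23 days. Type I error stays below 6% in the cases shown. The one marked loss of power, 10%/3%, gives the two-week rule alone the full 10% that the protocol allows for all loss. All of this stands, and it rules out any claim that a large bias is expected.

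Second, no section says that route changes the length of intubation, and post-operative care is meant to be standardised. The only pathway the text suggests, lighter nasal sedation, would remove more oral infants and so work against the trial's own hypothesis. That is fair. But standardised scores set the dose by need, and need is what the protocol expects to differ. Overstatement is not shown to be likely; it cannot be excluded either.

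Third, the clause in Study Procedures, item 2, is written for re-intubated infants. Such an infant may have fed orally in between, so the argument that only outcomes above 14 days are removed fails there. The wording of its two-week test also differs from that in the exclusion list. This narrows the argument about long outcomes; it does not change the fact that randomised infants are removed.

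Fourth, ECMO and CPR losses are disclosed and allowed for in the sample size. An allowance restores numbers, not comparability.

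Finally, an analysis plan not shown here might define an intention-to-treat set. It could not do so without contradicting the protocol's exclusion list.

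**Conclusion.** The concern holds and should be fixed before the primary analysis can be relied on. The protocol states a rule that removes randomised infants on post-operative events, one of which is closely tied to the primary outcome. The documents give no arm-specific rates, so neither the size nor the direction of bias can be stated. Under the assumptions shown, a true difference of 6 days becomes anything from 5.07 to 6.30, depending on how unequal removal is, and near-equal removal does little. The severity rests on the loss of the randomised comparison and on a result limited to infants who cannot be identified at intubation, not on these illustrative sizes.

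**What to change.** In the exclusion list, delete the two-week line and the post-operative part of the CPR and ECMO lines as grounds for removal from the study, together with the corresponding clause in Study Procedures, item 2. Follow all randomised infants to discharge and analyse them in the group assigned. The statement in Study Procedures, item 1, that failed nasal intubations are analysed as oral must be brought into line with this.

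The retained infants may die or go home without full oral feeds, and the planned t-test needs a number for every infant, so the protocol must state how they are counted. Infants retained under the present rules can also be discharged on tube feeds, so this rule is needed in any case. Report the set without ECMO, CPR of more than 5 minutes and two-week intubation as a labelled sensitivity analysis. None of this changes clinical care.

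The cost is a protocol amendment, continued chart follow-up of the retained infants (data collection already runs to discharge) and a check of power. With all 44 per group analysed and a 6-day difference, Welch power is 83.4% at the protocol's SDs. Very ill infants may widen the spread: if both SDs are 10% higher, power is 75.9%, and if 20% higher, 68.5%. Those increases are assumptions.

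### Tube feeding at discharge is tested without adjustment after unstratified allocation, although the protocol names single-ventricle physiology as a risk factor for feeding procedures

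*Protocol*

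**What the plan says.** All references are to the protocol, the only document at hand.

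- **Allocation** (Statistical Considerations, item 1). The form asks for the stratification or randomisation scheme. The answer is that infants are "randomized to oral or nasal intubation using a block randomization scheme generated by a UVA statistician to generate equally sized oral and nasal groups". No stratification factor is named. Enrolment is "44 participants per group, for a total of 88", and the analysis needs 40 per arm.
- **Reliance on chance balance** (item 4). "While we anticipate that the randomization will balance the distribution of these covariates between the groups", covariates are still offered in a negative binomial model of feeding time. The RACHS score is the only one named. The first analysis of feeding time is an unadjusted t-test.
- **Secondary outcomes** (item 5). Length of stay is analysed like feeding time, so adjustment is available there. For tube feeding: "The chi-square tests will be used to compare the proportion of participants in each group requiring tube feeding at discharge". No adjusted comparison is described for that outcome.
- **Prognostic evidence** (Background). From a retrospective series of 83 infants: "Single ventricle physiology and presence of a shunt were additionally identified as risk factors for additional feeding procedures". In that series 9.6% needed invasive feeding procedures. From a retrospective series of 79 infants after the Norwood procedure: "Of these patients, 59.5% required gastrostomy tube placement for feeding before discharge". A laryngoscopy study gives gastrostomy rates of 18% after Norwood and 11% after biventricular arch repair.

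**The concern.** Blocking equalises the number of infants per arm and does nothing for case mix. If single-ventricle status strongly predicts tube feeding, two things follow in a trial of this size. First, variation in tube feeding that the factor explains stays in the error term of the chi-square test and costs power. Second, a chance excess of single-ventricle infants in one arm shifts the observed difference, and no described analysis of this outcome takes that into account. Feeding time and length of stay are better placed because they have a covariate model, but single-ventricle status is not named among its covariates.

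**Working it through.** **The plan's own figure.** The protocol states 80% power with 40 per arm for a 6-day difference in feeding time. Taking the 6 days as a reduction (means 13.5 and 7.5) with a common coefficient of variation (11.7/13.5 = 0.867, so SDs 11.7 and 6.5), the unequal-variance t-test gives 79.7%. The figure reproduces, and 40 x 1.1 = 44 as stated. The protocol gives no power figure for tube feeding, so the rest needs assumptions.

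**Inputs.** 44 per arm enrolled and 40 analysed (protocol). Gastrostomy or feeding-procedure rates of 59.5%, 9.6%, 18% and 11% (Background). Single-ventricle share p of 20-50% (assumption; the protocol gives none).

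**Step 1: chance imbalance.** With K single-ventricle infants among 88, the number X in one arm is hypergeometric and the between-arm difference is D = (2X - K)/44. For K = 26: Var(X) = 44 x 0.2955 x 0.7045 x 44/87 = 4.63, SD(X) = 2.15, SD(D) = 2 x 2.15/44 = 9.8 points.

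| Assumed share | SD of imbalance (points) | P(10 points or more) | P(15 points or more) |
|---|---|---|---|
| 20% (K = 18) | 8.6 | 19% | 6% |
| 30% (K = 26) | 9.8 | 24% | 10% |
| 40% (K = 35) | 10.5 | 38% | 19% |
| 50% (K = 44) | 10.7 | 29% | 14% |

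The 19% owes much to discreteness. With 35 infants only odd differences occur, and 7/44 = 15.9 points just clears the cut. At a 16-point cut it is 8.1%.

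**Step 2: effect of an imbalance on tube feeding.** Shift = imbalance x risk gap.

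- Strong contrast: 15 x (0.595 - 0.096) = 7.5 points.
- Weak contrast: 15 x (0.18 - 0.11) = about 1 point, against a standard error of about 7.5 points.

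**Step 3: variance explained.** R-squared = p(1-p) x gap^2 / [P(1-P)], where P is the overall risk.

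- Strong contrast, p = 0.3: P = 0.3 x 0.595 + 0.7 x 0.096 = 0.246, and R-squared = 0.21 x 0.249/0.185 = 0.28. Over p = 0.2 to 0.5 the range is 0.25-0.29.
- Weak contrast, p = 0.5: P = 0.145, and R-squared = 0.25 x 0.0049/0.124 = 0.01.

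**Step 4: type I error of the planned chi-square test** (simulated, 40 per arm, unstratified).

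- Strong contrast: 4.8-5.0% overall. This averages about 2% when the arms are balanced and about 7-8% at a 15-point imbalance.
- Weak contrast: 5.5% overall, and 5.7% when the imbalance is 15 points or more.

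**Step 5: power on tube feeding** (simulated, 40 per arm, illustrative within-stratum odds ratio 0.30). The change is from the chi-square test to Mantel-Haenszel without continuity correction, both on unstratified allocation.

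- Strong contrast: gain of about 4-9 points.
- Intermediate contrasts: gain of about 0-3 points.
- Weak contrast: loss of about 3-4 points. Here the chi-square test runs slightly above 5%.

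For the strong contrast at a 30-40% share, power is 34-39% with the chi-square test on unstratified allocation and 42-48% with Mantel-Haenszel on stratified allocation. Nearly all of that gain comes from the adjusted analysis. Stratifying while keeping the unadjusted chi-square test would give about 2% rejection under the null in the strong contrast.

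**The case against.** The strongest reply is that nothing here is invalid. Simple blocked allocation is a legitimate choice for 88 infants at one site, and chance imbalance is already part of the sampling variance of a randomised comparison. That stands: overall type I error is about 5%. The 2% and 7-8% figures are slices conditional on the realised balance, not evidence of a faulty test.

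The second reply is that the large effect rests on a weak comparison. The 59.5% and 9.6% come from different series with different endpoints (gastrostomy; gastrostomy or fundoplication). The 9.6% is from a mixed series, not a biventricular one, and neither endpoint is the trial's NG-or-gastrostomy outcome. The only within-study contrast is 18% vs 11%, and its source reports similar vocal cord paralysis and aspiration in both repair types. This also stands, so the benefit is conditional.

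Third, the covariate list for feeding time is open-ended, the same methods apply to length of stay, surgical variables are collected, and an SAP not shown may add adjusted analyses. Finally, exclusions after randomisation and the analysis of failed nasal intubations in the oral group would erode any balance that stratification secured. Both points favour fixing the analysis before the allocation.

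What remains is that the protocol describes only an unadjusted test for the outcome closest to its own named risk factor.

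**Conclusion.** The point holds as an improvement in precision, of low to moderate priority. The planned test is valid but may waste power: about 4-9 points if single-ventricle status is as prognostic as the 59.5% vs 9.6% contrast suggests, and nothing if it is as weak as 18% vs 11%. The size rests on an assumed share of 20-50%, 40 analysed per arm and an illustrative odds ratio of 0.30.

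Three stronger readings are tempting and are not supported:

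- That a material imbalance is likely. A difference of 15 points or more arises in roughly 6-19% of trials, and even 10 points or more in only 19-38%.
- That single-ventricle status drives feeding outcome in general. The Background ties it to additional feeding procedures. For delayed transition to oral feeds, which is nearest the primary outcome, it lists RACHS score and prolonged intubation.
- That the sedation comparison is compromised in the same way. Its test is also unadjusted, but nothing in the protocol links single-ventricle status to sedative dose.

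**What to change.** 1. Pre-specify a comparison of tube feeding at discharge adjusted for planned single-ventricle versus biventricular repair: Mantel-Haenszel without continuity correction, or logistic regression with standardisation. Use the operation planned before randomisation.
2. Name the same factor among the covariates of the negative binomial models for feeding time and length of stay.
3. Optional, only if recruitment has not begun: have the statistician prepare two block lists by planned repair, and carry the stratum into the analysis. Without that last step the chi-square test would be conservative. Candidates are identified at the surgical conference and parents are usually approached in the week before surgery, so the planned repair should be known in time.

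Cost: items 1 and 2 are a few sentences and one analysis term, with a loss of about 3-4 points of power on tube feeding if the factor proves weak. Item 3 adds one set of envelopes and may leave the arms slightly unequal. The stated sample size does not change.
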